- Additional re-screening for screen failure and to confirm eligibility to participate in the clinical study can be performed in previously screened participants. The screening period may also be extended. Both re-screening and screening extension options should be discussed with the designated contract research organisation (CRO) study physician. Before randomisation, the principal investigator (PI) must ensure that all of the eligibility criteria are fulfilled. The investigator should confirm with the designated CRO study physician which option can be used.
- Home or Remote visit: Performed by a qualified Health Care Professional (HCP).

- Telemedicine visit: Remote contact with the participants using telecommunications technology including phone calls, virtual or video visits, and mobile health devices.
- At-home investigational product (IP) administration: Performed by a qualified HCP, except in Germany and France, where at-home administration of tezepelumab is not allowed. Additional information related to the visit can be obtained via telemedicine.

For further details on study conduct during civil crisis, natural disaster, or public health crisis, refer to Appendix C.

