6.2.3 Dose Administration

The investigator or authorised delegate will assess the injection site as per standards of medical care. For WOCBP, a urine pregnancy test will be performed, and first study intervention administration will be done when the result of the test is negative (Section 8.2.3).

[figure not shown]
The administration of tezepelumab should be recorded in the appropriate sections of the eCRF. Tezepelumab will be administered at the study site but at home administration by an HCP can also take place, if deemed necessary (see Appendix C). In case of at home administration, the HCP administering the dose will also fill out the source documentation to capture that the dose was successfully administered. Both the completed source documentation and the used device are to be returned to the site once the visit is completed for study intervention accountability.

The study intervention will be administered by the investigator/authorised delegate as specified in Table 1.

Each participant will receive tezepelumab 210 mg (one 1.91 mL injection), administered SC Q4W for 13 doses in the abdomen, thigh, or upper arm by APFS. The person administering the dose will wipe the skin surface of the upper arm, anterior thigh, or abdomen with alcohol and allow to air dry. The skin will be pinched to isolate the SC tissue from the muscle. The needle will be fully inserted at a 45-degree angle approximately into the SC tissue. The injection site should not be rubbed after each injection.

It is advised that the site of injection of the study intervention be rotated such that the participant receives study intervention at a different anatomical site at each treatment visit. The suggested injection site rotation sequence is presented in Figure 2.

Figure 2 Suggested Schema of Rotation of Injection Sites

After study drug administration

Participants should be observed for a minimum of 2 hours after administration of the first 2 study intervention administrations for the appearance of any acute drug reactions. For the remaining doses, participants will be observed for a minimum of 1 hour after study intervention administration for any such reaction.

Conditions that will require rescheduling of study drug administration

If any of the following should occur, the study intervention should not be administered:

- The participant received allergen immunotherapy injection on the same day as scheduled study intervention administration.

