8.3.13 Management of IP-related Toxicities

Appropriate drugs, such as epinephrine, H1 and H2 antihistamines, and corticosteroids, as well as medical equipment to treat acute anaphylactic reactions, must be immediately available when IP is being administered. Study site personnel must be trained to recognise and treat anaphylaxis (Lieberman et al, 2010). Details on anaphylaxis management are provided in Appendix G.

Anaphylaxis will be defined as a serious reaction that is rapid in onset and may cause death (Sampson et al, 2006). Anaphylaxis typically manifest as 1 of 3 clinical scenarios:

- The acute onset of a reaction (minutes to hours) with involvement of the skin, mucosal tissue or both and at least one of the following: a) respiratory compromise; or b) reduced blood pressure (BP) or symptoms of end-organ dysfunction
- Two or more of the following that occur rapidly after exposure: involvement of the skin/mucosal tissue, respiratory compromise, reduced BP or associated symptoms and/or persistent gastrointestinal symptoms
- Reduced BP after exposure.

Participants will have had a pre-assessment (ie, lung function) prior to IP administration. At Visits 2 and 3, participants should be observed for a minimum of 2 hours after IP administration for the appearance of any acute drug reactions. For the remaining visits involving IP administration, participants will be observed for a minimum of 1 hour after IP administration for any such reaction.

If an anaphylactic reaction occurs, a blood sample will be drawn from the participant as soon as possible after the event, at 60 minutes \pm 30 minutes after the event, and at discharge for analysis of serum tryptase. The sample will be tested at the local laboratory or central laboratory where applicable.

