C 3 Home or Remote Visit to Replace On-site Visit (Where Applicable)

A qualified HCP from the study site will visit the participants home/or other remote location as per local SOP, as applicable. Supplies will be provided for a safe and efficient visit. The qualified HCP will be expected to collect information per the CSP.

C 4 Telemedicine Visit to Replace On-site Visit (Where Applicable)

In this appendix, the term telemedicine visit refers to remote contact with the participants using telecommunications technology including phone calls, virtual or video visits, and mobile health devices.

During a civil crisis, natural disaster, or public health crisis, on-site visits may be replaced by a telemedicine visit if allowed by local/regional guidelines. Having a telemedicine contact with the participants will allow AEs, concomitant medication, ePRO and other assessments at the discretion of the PI to be collected and entered on the source documents.

C 5 At-home or Remote Location IP Administration Instructions

Note: This section is not applicable for Germany and France.

If a site visit is not possible, at-home or remote location administration of IP may be performed by a qualified HCP, provided this is acceptable within local regulation/guidance, or by the participant or his/her caregiver. The option of at-home or remote location IP administration ensures participants safety in cases of a pandemic where participants may be at increased risk by travelling to the site/clinic. This will also minimise interruption of IP administration during other study disruptions, eg, site closures due to natural disaster.

Note: Before initiating consent for home IP administration visit during study disruptions due to cases of civil crisis, natural disaster, or public health crisis, the participant must have received at least the first 3 IP administrations at the site.

Site must contact the participant by telephone to assess possible COVID-19 symptoms before initiating home visit.

C 5.1 At-home or Remote Location IP Administration by a Qualified HCP

Note: This section is not applicable for Germany and France.

A qualified HCP from the study site may administer the IP at the participant's home or other remote location according to the CSP. All necessary supplies and instructions for administration and documentation of IP administration will be provided. Additional information related to the visit can be obtained via a telemedicine or home visit.

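### Appendix C 5 lets the participant or a caregiver give the home dose, whereas every other home-dosing provision in the protocol assumes a health care professional

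*Protocol*

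**What the plan says.** Appendix C 5 deals with dosing when a site visit is impossible because of a civil crisis, natural disaster or public health crisis. It names a qualified HCP as a possible administrator and then adds "or by the participant or his/her caregiver".

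Section 4.1.1 lists the mitigation options for the same situation. Its entry for at-home dosing reads "Performed by a qualified HCP, except in Germany and France", and the section sends the reader to Appendix C for detail. Section 6.2.3 says that "at home administration by an HCP can also take place" and also points to Appendix C.

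The only home-dosing subsection of Appendix C is C 5.1. It is titled for, and limited to, a qualified HCP from the study site, who may dose at the participant's home "or other remote location according to the CSP".

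Two safety rules bear on home doses. Section 6.2.3 states: "For the remaining doses, participants will be observed for a minimum of 1 hour after study intervention administration". Section 8.3.13 repeats that observation period. It also says that drugs and equipment for acute anaphylaxis "must be immediately available when IP is being administered", and adds: "Study site personnel must be trained to recognise and treat anaphylaxis".

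**The concern.** A site that activates Appendix C in a crisis has to know who is allowed to inject. The body of the protocol says an HCP. The appendix to which the body refers adds two further kinds of administrator and gives no procedure for either.

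What is at stake is conduct and participant safety. If a site took C 5 literally and let a participant or caregiver inject with nobody else there, the protocol would offer no means of observing the participant for an hour or of treating an anaphylactic reaction at once.

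**Working it through.** The plan gives no figure on this point, so the check is a comparison of the provisions on home dosing.

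**Who injects**
- Section 4.1.1: a qualified HCP.
- Section 6.2.3: an HCP, who also completes the source record for the dose.
- Section 6.2.6: if a replacement device is needed, the HCP goes back to the site for it.
- Section 6.4: the dose comes directly from the investigator or designee, under medical supervision.
- Appendix C 5.1: a qualified HCP from the study site.
- Appendix C 5: a qualified HCP, the participant or a caregiver.

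Five provisions point one way, and the added clause in C 5 is the outlier. It is in the current text, not in an amendment log.

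**Whether the text can be reconciled**
- The introduction to Appendix C says that instructions on performing the procedures will be given at implementation. That covers how to dose. It does not say which of the two answers on who may dose is correct.
- Appendix C 3 states: "A qualified HCP from the study site will visit the participants home/or other remote location". C 5 itself refers to a home administration visit and to a telephone check for COVID-19 symptoms before it. C 5 can therefore be read as the participant or caregiver injecting while an HCP is present. On that reading the safety rules can be met, and only the conflict over who injects remains.
- C 5 does not require an HCP to be present on the participant or caregiver route, so dosing with no HCP there is also a possible reading. On that reading there is no stated way to meet the rules in Sections 6.2.3 and 8.3.13.

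**How far the clause can reach**
- Doses: 13 are planned, every 4 weeks from Week 0 to Week 48. C 5 requires at least the first 3 (Weeks 0, 4 and 8) on site. That leaves 13 − 3 = 10 eligible doses, at Weeks 12 to 48, all under the 1-hour observation rule.
- Places: SAP Section 4.1.1.1 lists 3 + 5 + 2 + 2 = 12 countries or territories. C 5 excludes Germany and France, leaving 12 − 2 = 10.
- Conditions: a declared disruption, sponsor notification with instructions, local permission (Appendix C introduction) and reconsent (C 1).

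These are limits on eligibility. The documents give no disruption length and nothing on how often a non-HCP would inject, so no count of affected doses follows from them.

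**The case against.** The strongest reply is that this is an editorial mismatch with no demonstrated consequence. Appendix C exists to change normal procedures in a crisis, and Sections 4.1.1 and 6.2.3 both defer to it. C 5 states a purpose, which is to protect participants and limit interruption of dosing, so the clause may be deliberate. The sponsor must issue instructions before any use, which is when a site would need the injector clarified. Section 6.4 argues against unsupervised dosing. Section 8.3.13 does not expressly require a trained person at a home dose, and its references to visits and lung-function pre-assessment suggest that it was written for the clinic.

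Much of this stands. The documents do not show which text the sponsor intended, so both repairs must be open to it. Unattended dosing is one reading only, and nothing shows that C 5 was ever activated. Deletion would also leave a separate tension: Section 6.2.2 wants the dose prepared by a qualified person at the site, which is awkward even for an HCP dosing at home.

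What does not stand is the suggestion that nothing needs changing. Later instructions can supply a method, but the approved text would still contradict itself on who may inject. The observation and anaphylaxis rules also contain no exemption for home doses.

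A reader might infer more than the documents support:
- *That the protocol sanctions unattended injection.* C 3, the visit wording in C 5 and Section 6.4 all weigh against treating this as settled.
- *That C 5.1 is the protocol's only home-dosing procedure.* Sections 6.2.3 and 6.2.6 also give home-dosing steps, although for an HCP.
- *That there is a documentation gap.* C 6 foresees data captured by the participant.
- *That a given share of doses is affected.* Any such percentage would count all doses falling in an assumed disruption, not doses given by a non-HCP.

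**Conclusion.** The inconsistency is real and minor. C 5 conflicts with Sections 4.1.1, 6.2.3, 6.2.6 and 6.4 and with C 5.1 on who may give a home dose. That conclusion rests on the text alone. The safety consequence is conditional: it needs C 5 to be activated and then read as dosing with no HCP present. Section 2.3 limits its weight further, since it reports no serious allergic or anaphylactic reactions judged related to tezepelumab in phase 2 and 3.

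The number of doses involved cannot be estimated. There is no effect on the estimand or the statistical analysis. SAP Section 4.1.9.2 tabulates doses by location, not by who injected. This is a desirable correction, not a necessary one.

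**What to change.** Delete "or by the participant or his/her caregiver" from Appendix C 5, so that home dosing is by a qualified HCP throughout. A cross-reference in C 5.1 to the rules in Sections 6.2.3 and 8.3.13 would help but is optional, because C 5.1 already requires dosing in line with the protocol.

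The cost is one clause in a protocol amendment, with no change to data collection, sample size or analysis. The downside is that a dose may be skipped in a crisis when no HCP can attend. One skip lengthens the interval from 4 to 8 weeks, and two in a row make it 12. How often this would happen cannot be known from the documents. Section 6.2.3 already has a skip rule, with contact to the CRO study physician after two consecutive skips, although it is written for other causes such as illness, fever and vaccination timing.

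If the sponsor does intend participant or caregiver dosing, it should instead align Sections 4.1.1, 6.2.3 and 6.4 with C 5 and add a C 5.2 stating how the 1-hour observation and immediate emergency treatment are provided. That keeps the route open but takes more drafting.

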Appendix D Estimated Oral Corticosteroid Dose Therapy Equivalence

Oral corticosteroid	Approximate equivalence dose
Prednisone	10 mg
Prednisolone	10 mg
Cortisone	50 mg
Hydrocortisone	40 mg
Methylprednisolone	8 mg
Triamcinolone	8 mg
Betamethasone	1.2 mg
Dexamethasone	1.5 mg
Deflazacort	12 mg

For conversions of other OCS doses or other OCS products, please see local label of OCS product or online conversion calculators (eg, https://clincalc.com/corticosteroids/).

Appendix E Prednisone/Prednisolone Doses < 5 mg in Relation to Available Oral Formulations*

Desirable daily dose	Available tablet strength	Administered number of tablets and frequency	
1 mg	1 mg	1 tablet each day	
1 mg	5 mg	1/4 tablet each day or 1/2 tablet every other day	
2 mg	1 mg	2 tablets each day	
2 mg	5 mg	½ tablet each day, or 1 tablet every other day	
2.5 mg	1 mg	If divisible – 2½ tablets each day If non-divisible – dose over 2 days as follows: 2 tablets on day 1 and 3 tablets on day 2	
2.5 mg	5 mg	½ tablet each day, or 1 tablet every other day	
3 mg	1 mg	3 tablets each day	
3 mg	5 mg	½ tablet each day, or 1 tablet every other day	
4 mg	1 mg	4 tablets each day	
4 mg	5 mg	1 tablet each day	

^{*}Liquid or tablet formulations may be used. The table above is to be used for tablet formulations. For liquid formulations, please provide a dispenser or dosing cup, if not provided with the bottle; this will allow the patient easy access to the desirable daily dose.

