8.1.2 OCS Dose Titration

At screening visit, participants will continue with or be switched to prednisone/prednisolone. For participants not previously receiving prednisone/prednisolone as OCS, the conversion table shown in Appendix D will be used to calculate the equivalent prednisone/prednisolone dose for dose titration.

The OCS dose titration in the reduction phase will be followed as per Table 7 depending on the initial OCS dose and HPA axis evaluation. Note: For participants who must reduce OCS dose more frequently than Q4W or if the scheduled dose reduction does not coincide with a clinic visit (see reduction scheme in Table 7), OCS dose reduction may occur remotely (eg, by telephone) instead of a clinic visit.

If Table 7 instructs to reduce dose by 5 mg increments, but the initial OCS dose is < 5 mg to the nearest dosing level, the 1st reduction would be smaller, rounding down to the nearest 5 mg, then continue on with 5 mg Q2W reductions (examples below):

- eg, $12.5 \rightarrow 10 \text{ mg} \rightarrow \text{etc.}$
- eg, $23 \rightarrow 20 \rightarrow 15 \rightarrow 10 \text{ mg} \rightarrow \text{etc.}$

• eg, $19 \rightarrow 15 \rightarrow 10 \text{ mg} \rightarrow \text{etc.}$

If Table 7 instructs to reduce the initial dose by 2.5 mg increments, but the initial dose is < 2.5mg to the next dosing level, the 1st reduction would be smaller, rounding down to the nearest 2.5 mg, then continue on with 2.5 Q4W reductions (examples below):

- eg, $8 \rightarrow 7.5 \rightarrow 5 \rightarrow \text{etc.}$
- eg, $6.25 \rightarrow 5 \rightarrow$ etc.

Investigators may also choose to slow the down-titration to 1 mg Q4W once the participant reaches an OCS dose of 5 mg/day based on participant symptoms.

For all participants, HPA axis integrity will be evaluated after 4 weeks on 5 mg/day and prior to tapering down the OCS dose (for participants with baseline OCS doses equal to 5 mg/day, this will be assessed 4 weeks after the first dose of tezepelumab administration and before initiation of the OCS reduction and maintenance phase). See Section 8.2.1 for details.

Table 7

OCS Dose Titration Schedule During the OCS Reduction and Maintenance Phase

Initial OCS	OCS down-titration to reach		an OCS dose of:		
dose/day					
	20 mg	10 mg	7.5 mg	5 mg	0 mg
> 20 mg	Reduction of 5 mg	Reduction of	2.5 mg of the	2.5 mg of the	No AI: reductions of 2.5 mg of the daily dose Q4W until reaching dose

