	of the daily dose	5 mg of the	daily dose Q2W	daily dose Q4W	of 0 mg/day
	weekly until	daily dose Q2W	until reaching	until reaching	Partial AI: reductions of 1 mg of the daily dose Q4W and repeat test
	reaching dose of	until reaching	dose of	dose of	2 months later ^a
	20 mg/day	dose of	7.5 mg/day	5 mg/day	Complete AI: No OCS dose reduction and repeat test 3 months later ^b
		10 mg/day			
$> 10 \text{ mg to} \le 20 \text{ mg}$		Reduction of	2.5 mg of the	2.5 mg of the	No AI: reductions of 2.5 mg of the daily dose Q4W until reaching dose
		5 mg of the	daily dose Q2W	daily dose Q4W	of 0 mg/day
		daily dose Q2W	until reaching	until reaching	Partial AI: reductions of 1 mg of the daily dose Q4W and repeat test 2
		until reaching	dose of	dose of	months latera
		dose of	7.5 mg/day	5 mg/day	Complete AI: No OCS dose reduction and repeat test 3 months later ^b
		10 mg/day			
> 7.5 mg to			2.5 mg of the	2.5 mg of the	No AI: reductions of 2.5 mg of the daily dose Q4W until reaching dose
≤ 10 mg			daily dose Q2W	daily dose Q4W	of 0 mg/day
			until reaching	until reaching	Partial AI: reductions of 1 mg of the daily dose Q4W and repeat test
			dose of	dose of	2 months later ^a
			7.5 mg/day	5 mg/day	Complete AI: No OCS dose reduction and repeat test 3 months later ^b
$> 5 \text{ mg to} \le 7.5 \text{ mg}$				2.5 mg of the	No AI: reductions of 2.5 mg of the daily dose Q4W until reaching dose
				daily dose Q4W	of 0 mg/day
				until reaching	Partial AI: reductions of 1 mg of the daily dose Q4W and repeat test 2
				dose of	months later ^a
				5 mg/day	Complete AI: No OCS dose reduction and repeat test 3 months later ^b
5 mg					No AI: reductions of 2.5 mg of the daily dose Q4W until reaching dose
					of 0 mg/day
					Partial AI: reductions of 1 mg of the daily dose Q4W and repeat test
					2 months later ^a
					Complete AI: No OCS dose reduction and repeat test 3 months later ^b
a Partial AI cortisol test	ing confirmed with A(CTH stimulation tes	ting or the alternativ	ve method described	Partial AI contismed with ACTH stimulation testing or the alternative method described in Amendix M. After renetition of the test 2 months later the decision to

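### Appendix E gives 5 mg/day for a 4 mg dose when only 5 mg tablets are available, so the slow taper begins with no reduction and then a 2.5 mg drop

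*Protocol*

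**What the plan says.** Table 7 (Protocol 8.1.2) sets two speeds below 5 mg/day. For partial AI: "Partial AI: reductions of 1 mg of the daily dose Q4W and repeat test" at 2 months. For no AI: "No AI: reductions of 2.5 mg of the daily dose Q4W until reaching dose" zero. Tables 3 and 8, section 8.2.1.2 and Appendix M use the same 1 mg pace for partial AI. Section 8.2.1.1 uses it for normal cortisol with signs or symptoms of AI. Section 8.1.2 also makes it an option on symptoms: "Investigators may also choose to slow the down-titration to 1 mg Q4W once the participant reaches an OCS dose of 5 mg/day".

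For doses below 5 mg where the exact strength is not available, section 8.1.2 allows alternate-day dosing averaged over two days and points sites to Appendix E. The 5 mg-tablet rows there are:

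- 4 mg: "1 tablet each day", with no alternative.
- 3, 2.5 and 2 mg: half a "tablet each day, or 1 tablet every other day".
- 1 mg: "1/4 tablet each day or 1/2 tablet every other day".

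The footnote permits liquid as well as tablets and adds: "The table above is to be used for tablet formulations". No row is marked as approximate.

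**The concern.** The 4 mg row does not deliver a dose below 5 mg. A site with only 5 mg tablets that follows the table leaves the participant on 5 mg/day for the first 4-week step, then moves to 2.5 mg/day at the second. The slow taper exists to separate partial AI from no AI, and at this point the two become the same size of step. The participants concerned have just been shown to have impaired adrenal reserve, or have symptoms that led the investigator to slow down.

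**Working it through.** **Inputs.** Tablet strength 5 mg; tablet counts from Appendix E; two-day averaging from section 8.1.2; nominal taper 5-4-3-2-1-0 in 4-week steps from Table 7 (partial AI).

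**Delivered dose** = tablets per day × 5 mg, averaged over two days.

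| Desired (mg/day) | As printed | Delivered (mg/day) | Error (mg) |
|---|---|---|---|
| 4 | 1 daily | 5 | +1.0 |
| 3 | 1/2 daily | 2.5 | −0.5 |
| 2.5 | 1/2 daily | 2.5 | 0 |
| 2 | 1/2 daily | 2.5 | +0.5 |
| 1 | 1/4 daily | 1.25 | +0.25 |

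Only the 2.5 mg row reproduces its stated dose.

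**Was a closer dose available?** With n half tablets over two days the average is 2.5n/2 = 1.25n mg/day, that is 1.25, 2.5, 3.75 or 5. The nearest values to 4, 3, 2 and 1 mg are 3.75, 2.5, 2.5 and 1.25. The printed 3, 2 and 1 mg rows already use them. Only the 4 mg row does not: its error is 1.0 mg, against 0.25 mg for 3.75 mg/day.

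**First two steps.**

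- Planned 5-4-3: drops of 1 and 1 mg; the second is (4−3)/4 = 25%.
- Printed 5-5-2.5: drops of 0 and 2.5 mg; the second is (5−2.5)/5 = 50%.
- With 3.75 mg for the 4 mg row, 5-3.75-2.5: drops of 1.25 and 1.25 mg; the second is (3.75−2.5)/3.75 = 33%.

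**Timing.** If the first step is taken at the partial-AI result, the 2.5 mg drop comes at week 4, before the 2-month retest. If the first step is taken 4 weeks later, it comes at week 8, at the retest.

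**Exposure over those two steps** (28 days each).

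- Planned: (4 + 3) × 28 = 196 mg.
- Printed: (5 + 2.5) × 28 = 210 mg, 14 mg more.
- Revised row: (3.75 + 2.5) × 28 = 175 mg, 21 mg less.

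**If the slow taper runs to the end.** Printed: 5-5-2.5-2.5-1.25-0. Revised row: 5-3.75-2.5-2.5-1.25-0. Exposure over the four non-zero steps is 10 × 28 = 280 mg planned, 11.25 × 28 = 315 mg printed and 10 × 28 = 280 mg revised. Zero comes at the fifth step in each case. This full path is conditional. Under the Table 7 footnotes, a normal retest allows a direct drop to zero from 3 mg or less, and complete AI halts the taper.

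**The case against.** The rounding may be deliberate. The amendment summary says Appendix E was revised to fit the titration schedule and to cope where 1 mg tablets are not available. The identical 2, 2.5 and 3 mg instructions make the approximation visible, and the protocol states no nearest-dose rule. This explains why the rows are approximate. It does not explain a 4 mg row that repeats 5 mg when 3.75 mg is within reach.

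The body text also leaves room: alternate-day dosing is allowed, so a site could improvise 3.75 mg/day, and liquid gives exact doses. That limits how many participants are affected but does not correct the row sites are sent to.

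Two points about the remedy stand in full. It puts participants below the planned dose in both early steps, whereas the printed table gives more steroid than planned over the same period. It also does not delay the arrival at 2.5 mg/day, which still comes at the nominal 3 mg step.

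Safeguards exist as well. Section 8.2.1.3 requires symptom education and steroid emergency cards for any partial or complete AI. Without evidence of HPA recovery it adds warning identification and a medical report, and it recommends corticosteroid supplementation under stress. Adrenal crisis is an adverse event of special interest.

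A reader might infer that the table withdraws steroid faster than planned overall. The documents do not support this: printed exposure is higher than planned over the first two steps, and the delivered dose is never more than 0.5 mg/day below plan.

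**Conclusion.** The 4 mg row for 5 mg tablets is wrong as written. It turns the first two 1 mg steps of the slow taper into no reduction followed by a 2.5 mg (50%) drop, the step Table 7 gives to participants with no AI. This rests on a site having neither 1 mg tablets nor liquid and following Appendix E literally. The documents do not say how many participants that covers.

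It would be tempting to conclude that the efficacy results are compromised. They are not on this account: 4 and 5 mg/day both meet the 5 mg threshold, and zero is reached at the same nominal step if the taper runs through. Dose recording is not at issue either, because Protocol 8.1.2 and 9.4.3.1 and SAP 3.3 all use an average daily amount. With the AI safeguards in place, this is a minor dosing-table correction that should be made.

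**What to change.** Change the 4 mg row for 5 mg tablets to one tablet alternating with half a tablet (3.75 mg/day), or three-quarters of a tablet daily where it can be quartered. Mark the 1, 2, 3 and 4 mg rows for 5 mg tablets as approximate. State a preference for 1 mg tablets or liquid for any 1 mg taper. Leave the 1, 2 and 3 mg instructions as they are.

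The cost is one table row, one footnote and a letter to sites. Tablet splitting becomes slightly more complex, though no finer than the 1 mg row already needs. Appendix E already uses an unequal two-day cycle for 2.5 mg with non-divisible 1 mg tablets ("2 tablets on day 1 and 3 tablets on day 2").

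The lower early exposure, 175 mg against 196 mg planned, should be stated openly when the change is made. Where tablets can be quartered, alternating 3/4 with 1/2 for 3 mg (3.125 mg/day) is an option that brings it to (3.75 + 3.125) × 28 = 192.5 mg.
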